- *Hospital Anxiety and Depression Scale (HADS)*: Brief, 14-item highly validated scale for measuring anxiety (7 items) and depression (7 items), where scores of >8 for either anxiety or depression indicate probable symptoms.³ The HADS was selected due to its use in prior peer mentoring studies and strong psychometric profile
- *Modified Unified Parkinson's Disease Rating Scale (MDS-UPDRS)*: The motor subscale will be conducted by the PI or study staff, assessing rigidity, resting/postural/intention tremor,

bradykinesia, gait, and balance.

- *Montreal Cognitive Assessment (MoCa)*: a screening instrument designed to help health professionals detect mild cognitive dysfunction. It assesses numerous cognitive domains: attention and concentration, executive functions, memory, language, visuoconstructional skills, conceptual thinking, calculations, and orientation.
- *Patient Global Impression of Change (PGIC)*: This single-item rating scale asks subjects to rate their overall response to the intervention using a 7-point rating scale, with the options of “very much improved”, “much improved”, “minimally improved”, “no change”, “minimally worse”, “much worse” and “very much worse”. Recommendations for assessing importance of this scale include reporting the percentages of subjects endorsing each of the 7 response options.
- *Physical Activity Group Environment Questionnaire (PAGEQ)*: a measure of group cohesion used in sports psychology. This conceptual model of cohesion is a modified version of the GEQ (Group Environment Questionnaire). PAGEQ is divided into two levels of perceptions: an individual’s perspective of a group as a whole (collective) and an individual’s attraction to a group (personal). These two levels are further defined by social and task aspects. All these components are categorized into four constructs: Group Integration-Social (GI-S), Group Integration-Task (GI-T), Individual Attractions to the Group-Social (ATG-S), and Individual Attractions to the Group-Task (ATG-T).
- *Parkinson’s Disease Questionnaire- Short Form (PDQ-8)*: A validated and shortened version of the PDQ-39, with 8 items each representing one domain of the PDQ-39, also with a summary index score standardized to a scale of 0-100, with higher scores signifying worse quality of life; this scale is recommended for use in PD by the Movement Disorder Society.
- *Symbol Digit Modalities Test*: This uses a reference key while the examinee has 90 seconds to pair specific numbers with given geometric figures. Responses can be written or oral, and for either response mode, administration time is 5 minutes. The WPS AutoScore Test Form simplifies scoring. SDMT allows the opportunity to compare written and spoken responses from the same individual. The Manual provides separate norms for written and oral administrations of the test. Norms for adults are separated by age group and level of education.
- *Digit Span Test*: This tests the number of digits a person can absorb and recall in correct serial order after hearing them or seeing them. Here the person has to remember a small amount of information for a relatively short time, and the order of recall is important. To test the auditory digit span of a person, the administrator says numbers slowly in one second intervals, in a monotone voice. For example, the administrator will say 6-1-5-8 and have the person repeat it back in the order it was given or the reverse order. If the person is able to say a 4 digit sequence back correctly 75% of the time on the first try, it will be considered a short term memory of 4, and is the same for each higher digit. The average in our society for a seven-year old to adult is 7.

III.b. Data Analysis and Data Monitoring

Oversight of the data will be maintained by the Principal Investigator. The Principal Investigator will

review study procedures annually and report any concerns in the IRB continuation application. This is a Level I, Low, Minimal Risk study; therefore, there is minimal risk of unanticipated problems with the exception of breaches in confidentiality. The data for the study will be entered into a secured database using an electronic data capture program, Research Electronic Data Capture (REDCap).²² The database will be stored on a secure password-protected server and not on individual desktop computers. The code sheet will be password protected and the password will be updated annually. Breaches of confidentiality will be reported to the IRB immediately with the “Reportable Event/Unanticipated Problem Form.”

Data will be exported from REDCap in de-identified format for statistical analysis, with all PHI stripped from the dataset prior to analysis by statisticians. We will summarize categorical variables by frequencies and percentages and will assess continuous variables for normality, summarized by mean/standard deviation, or median/interquartile range. We will report the basic descriptive statistics of the cohort, including baseline demographics, TUG, MDS-UPDRS, HADS, PDQ-8, IPAQ, SDMT, MoCa, and DST. We will report on attendance, defined as the percentage of classes attended, in each arm once active. We will analyze the change in TUG, MDS-UPDRS, HADS, PDQ-8, IPAQ, SDMT, DST, MoCa, and PAGEQ respectively, from baseline to six months, comparing Arm 1 and 2 (active vs. control), and again at twelve months to determine whether longer participation yields additional benefits, using paired *t*-tests or nonparametric Wilcoxon sign rank tests, as appropriate. We will report on the percentage of subjects endorsing each of the 7 PGIC response options at six and twelve months, between Arms, respectively. We will report the descriptive statistics concerning whether subjects’ individual predefined goal for the class was achieved (binary outcome), and will present de-identified qualitative comments noted in the feedback at the study visit focus groups. We will report descriptive statistics on continued interest and likelihood of recommending the program to someone else with PD. We will analyze descriptive statistics on continued involvement in karate/martial arts, and will again report the percentage of subjects endorsing each PGIC response option.

The qualitative data from the study visit focus groups will be audio-recorded and transcribed, with all identifying information stripped from the transcripts. Once transcribed, the audio recordings will be destroyed. The qualitative data will be analyzed using a grounded theory approach to identify pertinent themes, with data stored as password-protected files behind the Rush firewall, accessible only to study staff.

All video footage will be the sole property of the PI. Videos will have identifying information (i.e. image of patient’s face, first name). Video files will be stored and password-protected behind the Rush and the Columbia firewalls. The video along with the data collected from the focus groups and karate classes may be used as part of the dissemination of the study results and for educational purposes.

The PI, co-investigators, and/or study staff will review all data collection forms on an ongoing basis for data completeness and accuracy as well as protocol compliance. To maintain blinding, the Research Coordinator will maintain a codesheet linking the subject ID numbers and subject names, which will be password-protected. The PI will only break the blind in the event of a safety concern. The data will be reviewed on a quarterly basis:

- Subject accrual (including compliance with enrollment criteria)
- Status of all enrolled subjects
- Adherence data regarding study visits and procedures

Safety data (AEs and SAEs) will be reported to the Principal Investigator and reviewed per occurrence and in accordance with the IRB's regulations. Any significant findings (i.e. protocol deviations) will be reported to the IRB in accordance with requirements and will be documented accordingly.

III.c. Data Storage and Confidentiality

All subjects will be assigned unique ID numbers. All research data files will be stored at the Rush University Parkinson's Disease and Movement Disorders Program in secured file cabinets, including hard copies of case report forms, informed consent forms and informed consent documentation checklists. Data will be entered into a secured database (REDCap). The database will be stored on a secure password-protected server and not on individual desktop computers. The code sheet will be password protected and the password will be updated annually. Hard copies of case report forms and informed consent documentation checklists will be labeled with the study ID only and maintained in individual files by study ID number. Signed informed consent forms, containing subject names, will be stored separately in the regulatory binder, which will be stored in a locked file cabinet in the PI's office. Class attendance records will be maintained using name only, not subject ID, by the class instructors. These records will then be given to the Research Coordinator following the final class, who will then link the attendance information with the subjects' data using the code sheet. Attendance information will be entered into REDCap. Subject records will be kept for ten years in accordance with Rush policy, after which time, the hard copies/source documents will be destroyed, and the database will remain in its electronic format but with identifying information removed, anonymizing the data.

Only the PI and research staff will have access to the database and hard copies of study documents. Data will be stored in a format suitable for research inquiries by the PI who might make use of the data in a retrospective manner for other Rush-based research studies. If a particular researcher/collaborator has an interest in a study population, then the PI will review the database to identify eligible subjects that meet the study inclusion criterion and the potential participant(s) will then be contacted by a member of this study team whom the subject has already met to see if they are interested in participating in the particular study. If a participant is interested, he or she will be referred to that Rush study team and will be scheduled for a separate consent procedure with the individual Rush researcher for that particular study and at that point the participant can choose whether to participate or not in that particular study. The results of the Karate for PD study may be published in a book, journal, and other media or used for teaching purposes. However, all published data will be made anonymous.

IV. Risk/Benefit Assessment

IV.a. Risk

There are no known risks from participating in neurological or neuropsychological tests. Subjects may experience mild boredom or cognitive fatigue; however, most individuals with like symptoms find the tests interesting and are able to tolerate up to two-hour duration of testing well. There is, however, a risk of falls or injury associated with participation in any exercise, including karate, for which subjects assume the risk and liability as they would with participation in any voluntary exercise activity. The risks will be minimized to the extent possible by 1) having all instructors undergo basic instruction in principles of PD by the PI prior to the first class; 2) having all classes held at quieter times in the dojo, so as to avoid overcrowding and risks of falls or freezing of gait in crowded, busy situations; 3) having small instructor to subject ratios to allow for maximal supervision and guidance; 4) having study staff available by phone to answer any questions or address concerns.

Another possible risk is the loss of confidentiality by participating in the documentary because the subject's image may be captured. However full names will not be used during interviews with the subjects who agree to answer questions about their experiences with the karate classes.

IV.b. Potential Benefit to Subjects

Potential benefits to subjects include the following: 1) cognitive and physical improvements in PD symptoms related to both vigorous physical activity and mindful exercise; 2) benefits of mindful exercise on quality of life; 3) the enjoyment of participating in a new activity in a social environment with other individuals with PD; 3) the satisfaction of learning a new skill; 4) the knowledge that by participating, subjects are contributing to the understanding of how karate impacts individuals with PD; 5) the altruistic benefit of contributing to the development of a fun, novel intervention for themselves and potentially others. Additional benefits include the opportunity to be active in the community and form relationships with peers. The positive effects on subjects with PD also have the potential to impact the wellbeing of their families and caregivers, as this karate class offers a new option for fun, therapeutic activity. The potential benefits to society include furthering the involvement of individuals with chronic diseases in community activities and the potential physical benefits may help modify the disease progress for the many affected by PD.

V. Subject Identification, Recruitment, and Consent/Accent

V.a. Method of Subject Identification and Recruitment

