This is a randomized, single-blinded, crossover-controlled, one-year study of non-contact karate for early- to middle-stage PD. The karate classes are developed for and will include only people with PD. Eligible subjects will attend a baseline study visit at Rush University Medical Center. At that time, the study logistics will be reviewed, informed consent process will occur, and each subject will complete brief, individual pre-intervention assessments including a demographic and medical history questionnaire, followed by assessments of overall mobility, gait, and balance (instrumented Timed up and Go, I-TUG; instrumented 2-minute walk, I-WALK, and instrumented sway test, I-SWAY), PD-specific clinical characteristics (Movement Disorders Society Unified Parkinson's Disease Rating Scale, MDS-UPDRS), overall cognition (Montreal Cognitive Assessment, MoCA), executive function and attention (digit span test, DST, and symbol digit modality test, SDMT), anxiety and depression (Hospital Anxiety and Depression Scale, HADS), physical activity (International Physical Activity Questionnaire, IPAQ) and quality of life (PDQ-8). Instrumented gait analysis will be performed to gather more detailed data on stride length and velocity, number of steps to turn, turn duration, and postural sway.¹⁶

During recruitment, and confirmed by the Research Coordinator during the baseline visit, each subject will be asked to identify their preference for karate studio (dojo) location: Roscoe Village, Evanston, Glenview, Park Ridge, or Wilmette.

Once all subjects have completed the objective and subjective baseline assessments, the baseline visit will continue with a one-time, in-person, group training highlighting current research on the benefits of exercise for PD. This training will be delivered by the study team in collaboration with an experienced physical therapist familiar with evidence-based recommendations for safe and effective exercise programs for individuals with early to middle stage PD. Participants will leave the training with printed, publicly available materials on exercise for PD as references.

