After the training, eligible subjects will be grouped by dojo preference, and randomized 1:1 within each dojo into **Arm 1**: immediate participation in six months of twice-weekly karate classes, or **Arm 2**: usual exercise for six months. After six months, Arm 1 participants may opt to pay for dojo membership and continue classes, and Arm 2 participants will crossover and begin six months of twice-weekly karate classes. Only the Research Coordinator will know which subjects belong to Arm 1 and Arm 2, and she/he will deliver all study-related communication to the subjects.

The karate classes have been specifically designed for individuals with early- to middle-stage PD, focused on incorporating upper and lower limb movements in multiple directions, increasing awareness throughout the body, shifting body weight and rotation, relaxation of the muscles, improving reaction time, using complex repetitive actions to improve coordination, footwork training and centered weight shifts to help with fall prevention, and striking shields for self-defense and stress relief. The PI and study team will provide instruction on PD to all instructors prior to study launch, and will be available and responsive to any questions or concerns throughout the course of the study. The structure of the 6-

month curriculum will be identical at each of the five dojo locations. If a subject misses a class, they may choose to make up a class at one of the other dojo locations.

Every two months, subjects in both Arms will receive an online link to report their attendance at classes, indicate whether their PD medication regimen has changed (as a potential confounder), and complete the IPAQ, HADS, and PDQ-8. In addition, the survey will contain the Physical Activity Group Environment Questionnaire (PAGEQ) to measure camaraderie, and Patient Global Impression of Change (PGIC) for the subject's global impression of change. The online survey will be delivered through a secure online database called Research Electronic Data Capture (REDCap). The purpose of the online surveys is to track adherence to karate classes, adherence to other walking/moderate/vigorous activity, quality of life, anxiety, depression, global impression of change, and group cohesion.

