Our sample size calculation (see table below) is based on the results from the pilot study with the primary outcome being change in TUG. We powered our original study based on existing literature, in which the mean TUG score for individuals with PD is 14.8 seconds with standard deviation of 5.8 seconds, and minimum clinically important difference values for the TUG ranged from 2 seconds to 5 seconds in various studies.^{1,17} However, our pilot cohort had a pre-intervention baseline mean TUG of 9.6 seconds, standard deviation of 2.1. As per the tables below, if our new cohort has a similar baseline mean TUG, we would need 12 individuals in each arm to detect a difference of 2 seconds with 90% power, however this may not be plausible (i.e., 9 seconds may be close to the limit of how quickly anyone can complete the TUG task). If, however, participants have a more modest baseline to start, which may be expected when recruiting more broadly than at a tertiary referral center, we yield the second half of the table below. Here, we are extrapolating a baseline mean TUG of 12.5 with SD 4.0 (between our pilot data and the existing literature); with 19 individuals per arm, we would be 90% powered to detect a 3s difference between pre- and post-intervention TUG.

If we assume up to 25% attrition in this group of older adults with a chronic neurodegenerative disease, particularly in a longitudinal study over six months, we need to enroll 52 individuals (26 per arm) to yield a total of 40 completing the study.

Baseline mean TUG	Baseline SD TUG	Minimum clinically Important difference	Power	Sample size per arm
9.6	2.1	2s	.9	12
			.8	9
9.6	2.1	3s	.9	6
			.8	4
9.6	2.1	4s	.9	3
			.8	3
9.6	2.1	5s	.9	2
			.8	2
12.5	4.0	2s	.9	43
			.8	32

12.5	4.0	3s	.9	19
			.8	14
12.5	4.0	4s	.9	11
			.8	8
12.5	4.0	5s	.9	7
			.8	6

II.b. Gender of Subjects

There will be no exclusion of subjects based on gender.

II.c. Age of Subjects

Subjects will be 30-90 years of age.

II.d. Racial and Ethnic Origin

There will be no exclusion of subjects based on racial or ethnic characteristics. However, subjects must be fluent in English to participate in the karate classes, as that is the language of instruction, and due to the general lack of appropriately translated neurological and neuropsychological assessments and appropriate normative comparison samples. These factors are critical for accurate administration, scoring, and interpretation of neurological and neuropsychological test data.

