Subjects who are interested in participating based on review of printed or electronic recruitment materials will be directed to contact the Research Coordinator by phone, who will provide them with information about the study and the opportunity to ask questions about it in detail; those who express continued interest in participation will be screened for eligibility and ability to attend the scheduled classes, held at one of the five Fonseca Martial Arts dojos in Glenview, Wilmette, Park Ridge, Evanston, or Roscoe Village. Arm 1 will attend classes twice weekly for 6 months, with classes anticipated to run from January through June 2019. Afterwards, Arm 1 subjects may continue classes for a fee between July through December 2019 while subjects in Arm 2 crossover to the active portion and begin their six months of karate classes. Subjects can select from participating in either weekend/weekday daytime classes, or weekday/weekday evening classes, depending on their availability and proximity to each dojo's geographic location. Screening will occur on a rolling basis until the 52 participants are recruited.

Pre-Intervention Study Visit

All subjects will attend a pre-intervention study visit, at which time the study team, including Principal Investigator, Research Coordinator, and research assistants, will review the study design and flow, informed consent process, and each subject will be individually visited by a member of the study team to review and sign the informed consent form (ICF). No reconsenting will be necessary because Phase I participants will not be eligible to participate in Phase II, with the exception of participants who withdrew early from Phase I, who may enroll in Phase II provided that their reason for withdrawal no longer applies and these individuals will need to be newly consented with the Phase II consent document.

Subjects will complete a brief demographic and health questionnaire, including duration of PD diagnosis in years, current medication regimen, baseline activity level, prior involvement with karate or other martial arts, number of falls in the past 12 months, and subjects will complete the Parkinson's Disease Questionnaire-8 (PDQ-8)¹⁸, a brief, validated, PD-specific 8-item measure of quality of life. Subjects will complete the Hospital Anxiety and Depression Scale (HADS). Subjects will also write their response to the open-ended prompt, "What do you hope to achieve in this class?"

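### Randomisation is 1:1 within each of five dojos, but the Arm 1 versus Arm 2 comparison does not use dojo; adding it is a cheap improvement whose benefit is conditional and probably modest

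*Combined protocol and SAP*

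**What the plan says.** Section I.c asks each participant for a "preference for karate studio (dojo) location: Roscoe Village, Evanston, Glenview, Park Ridge, or Wilmette". After the baseline visit, "eligible subjects will be grouped by dojo preference, and randomized 1:1 within each dojo". The method that enforces 1:1 within a dojo (blocks, a list, or neither) is not given. Under the screening call in section III, class choice is described as "depending on their availability and proximity to each dojo's geographic location", so dojo also marks where people live.

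Section III.b is the only statistical analysis text. It takes the change in each continuous measure from baseline to six months, "comparing Arm 1 and 2 (active vs. control), and again at twelve months", "using paired *t*-tests or nonparametric Wilcoxon sign rank tests, as appropriate". It has no dojo term, stratified test or other covariate. It states no significance level and plans no confidence interval for the arm difference.

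The sample size in II.a "is based on the results from the pilot study with the primary outcome being change in TUG". It does not mention dojo. For the row that leads to 52 enrolled, the protocol states: "we are extrapolating a baseline mean TUG of 12.5 with SD 4.0".

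**The concern.** Balancing the arms within dojo takes between-dojo variation out of the difference between arm means. A test that ignores dojo leaves that variation in the estimated standard error. If dojo is related to the outcome, the analysis then claims less precision than the design delivered. About 40 completers are expected and power for a two-arm comparison is already short, so precision available at no extra recruitment should be used.

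There is also a coding risk. Make-up classes may be taken at another dojo (I.c), and Arm 2 later starts at a dojo of choice (section III, Six-month study visit). Unless the plan fixes which dojo counts, a stratum added later could be coded from what happened after randomisation.

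**Working it through.** **The plan's own figure.** Inputs from II.a: SD 4.0, difference 3 s, 90% power. Assumption: two-sided 5%, because the plan states no level. The pre-post (one-sample) formula n = (SD × (1.960 + 1.282) / difference)² gives (4.0 × 3.242 / 3)² = 18.7, so 19, as stated; 19 / 0.75 = 25.3, so 26 per arm and 52 in total. Dojo plays no part. A two-arm comparison needs twice 18.7 = 37.4, so 38 per arm. With 20 per arm, a two-sample t-test has about 64% power. That shortfall is a separate matter, but it is the baseline for the power figures below.

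**What is compared.** III.b names paired tests, which cannot compare two independent arms. The check therefore uses the two-sample t-test that a between-arm comparison would need, without and with a dojo term. Assumptions: 5 dojos with 4 completers per arm in each, total variance 1, and r = dojo's share of the variance in TUG change. The documents give no r, so a range is used.

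**Expected interval ratio.** With n = 20 per arm and m = 4 per dojo and arm, the within-arm sample variance picks up a fraction f = (n − m)/(n − 1) = 16/19 = 0.842 of the dojo variance. The variance the unadjusted test uses is (1 − r) + 0.842r; the correct one is 1 − r. The t quantiles are 2.024 (38 df) and 2.032 (34 df), ratio 0.996. So

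width without dojo / width with dojo ≈ 0.996 × √[(1 − 0.158r)/(1 − r)].

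- r = 0: 0.996
- r = 0.05: 0.996 × √(0.992/0.95) = 1.018
- r = 0.10: 0.996 × √(0.984/0.90) = 1.042
- r = 0.20: 0.996 × √(0.968/0.80) = 1.096

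**Simulation, balanced dojos, no class effect.** There were 40,000 trials per setting; a separate run of 15,000 is in brackets. Power is for 3 s / SD 4.0, a standardised difference of 0.75.

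| r | Type I error without dojo | Type I error with dojo | Width ratio | Power without → with dojo |
|---|---|---|---|---|
| 0 | 5.1% | 5.2% | 0.997 (0.997) | 63.9% → 63.6% |
| 0.05 | 4.7% (4.6%) | 5.2% | 1.018 (1.019) | 64.5% → 65.8% |
| 0.10 | 4.1% (4.2%) | 5.0% | 1.042 (1.041) | 65.3% → 68.2% |
| 0.20 | 3.4% (3.3%) | 5.1% | 1.095 (1.095) | 66.3% → 73.0% |

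The two runs differ by Monte Carlo error only.

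**Class effect in the karate arm only.** In the first six months only Arm 1 attends classes. Let c be the share of Arm 1 variance due to class or instructor, also assumed. Type I error without → with the dojo term:

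- r = 0, c = 0.05: 5.9% → 6.1%
- r = 0.05, c = 0.05: 5.5% → 6.0%
- r = 0.05, c = 0.10: 6.6% → 7.3%
- r = 0.10, c = 0.10: 5.9% → 7.2%

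The true variance of the difference is [2(1 − r) + c(m − 1)]/n. The unadjusted estimate averages [2(1 − r) − c + f(2r + c)]/n. They are equal when c/r = 2f/(m − f) = 1.684/3.158 = 0.53. Above that ratio the unadjusted test is too liberal, not too conservative.

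**No enforced balance.** With simple 50:50 randomisation within dojo, type I error without dojo is 5.0%, 4.9% and 5.1% at r = 0, 0.10 and 0.20: no conservatism.

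**The case against.** A reader might infer that the planned interval is definitely too wide, the test definitely too conservative, and the stated error rate wrong. The documents do not support that.

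- The plan states no error rate and no interval for the arm difference, so there is no stated figure to be wrong. The calculations also describe a two-sample test in place of the paired tests named.
- The direction is not settled. Instructor and class variation affects Arm 1 only, so it does not cancel between arms and it raises type I error. This stands. Against it, the curriculum is identical across dojos and make-up classes may be taken elsewhere, which may limit class effects; the documents do not quantify them.
- The dojo term alone can raise the error further when class effects exist, as the figures above show. This stands, and it is why the fix has a second part.
- Blocking within dojo is not stated. The natural reading of 1:1 within each dojo, with 26 per arm, is balanced allocation, but that is a reading.
- The relevant share may be small. The outcome is a change score, which already removes stable dojo differences in level, and baseline testing is at one centre. Nothing supports a share of 20% or more. At 5% the gain is about 2% of interval width and 1 point of power.

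None of this is a reason to leave out the factor by which participants are randomised. It limits what may be claimed for including it.

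**Conclusion.** The omission is in the text: dojo defines the randomisation and is absent from the analysis. The consequence is conditional. With balance within dojo, a real relation between dojo and TUG change, and no class effect, omitting dojo gives a type I error of about 4.6% to 3.3%, an interval about 2% to 10% wider, and power about 1 to 7 points lower, for assumed shares of 5% to 20%. At a share of zero there is essentially nothing to gain or lose. If karate classes differ in effect by more than about half the dojo share, the error runs above 5% instead. This is a low-cost improvement, not a fault that invalidates the comparison.

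**What to change.** In III.b, state that the continuous between-arm change comparisons (primary: six-month change in TUG) use a between-arm model with arm and the dojo used for randomisation. Say that this is not the dojo attended for make-up classes or the later dojo of choice. If a rank or permutation test is used, stratify it by, or permute within, the randomisation dojo. The PGIC can stay as reported percentages.

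Add a sensitivity analysis that allows for clustering by class in the karate arm, because the dojo term does not deal with it. With only five dojos, such an analysis will estimate class variance poorly and should be read as a check. State in I.c how 1:1 allocation within dojo is enforced.

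The cost is a few sentences and four degrees of freedom (38 to 34 with 40 completers). If dojo is not prognostic, the loss is under 1% of interval width with equal, balanced dojos, and about 2% with unequal dojos and random dropout. It would be larger if allocation within dojo were not balanced. With 8 per dojo the expected n₁n₀/N is (8 × 7/4)/8 = 1.75 instead of 2, against (40 × 39/4)/40 = 9.75 instead of 10 overall. The width then grows by about √[(2/1.75)/(10/9.75)] × 1.004 = 1.06, or 6%, at a share of zero. That is another reason to state the allocation method.

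### Until month 6 only Arm 1 is taught in study classes, yet the power and tests assume independent participants; any within-class correlation would make Arm 1's standard error too small and the stated power too high, probably by a modest amount

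*Combined protocol and SAP*

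**What the plan says.** Section I.c groups subjects by dojo preference, and they are then "randomized 1:1 within each dojo into" the two arms. Arm 1 gets "immediate participation in six months of twice-weekly karate classes". Arm 2 has usual exercise for six months and then crosses over to the classes. The curriculum is the same at all five dojos, and a missed class may be made up at another dojo. Section III (Screening Phone Call) offers a daytime or an evening schedule.

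Section II.a bases the sample size on change in Timed Up and Go (TUG), "extrapolating a baseline mean TUG of 12.5 with SD 4.0", and states that "with 19 individuals per arm, we would be 90% powered to detect a 3s difference between pre- and post-intervention TUG". After attrition it concludes: "we need to enroll 52 individuals (26 per arm) to yield a total of 40 completing the study". It gives no ICC, class size or design effect.

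Section III.b compares change from baseline to six months between the arms, and again at twelve months, using paired t-tests or "nonparametric Wilcoxon sign rank tests, as appropriate". No term for dojo, class or instructor appears.

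**The concern.** For the first six months the study itself creates groups in one arm only, which makes this a partially nested design. Arm 1 classmates share an instructor, a room and each other. The protocol expects the group to matter: camaraderie is among its opening aims, and cohesion is measured with the PAGEQ.

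A good or poor class would then move several Arm 1 results together. Counting those people as separate evidence understates Arm 1's variance. That raises the false-positive rate for the karate effect, narrows its interval and makes the planned power look better than it is. Randomizing within dojo does not remove the problem. It cancels what both arms share at a dojo, but not a class or instructor effect that reaches only Arm 1.

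**Working it through.** **Inputs from the documents.** Difference 3 s, SD 4.0 s, 19 per arm, 52 enrolled and 40 completing (20 per arm), five dojos. The 4.0 s is a baseline SD that II.a uses as if it were the SD of change; that use is kept here.

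**Assumptions.** Two-sided alpha of 0.05 (not stated in the plan). ICC of 0.02 to 0.10 (none is given). Class size 20/5 = 4 completers with one class per dojo, or 20/10 = 2 if every dojo ran both schedules. The between-arm test is taken to be a two-sample test of change, because the tests named in III.b are paired.

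**Step 1: reproduce the plan's figure.** A one-sample pre-post formula with independent observations gives n = [4.0 × (1.960 + 1.282)/3]² = 18.7, so 19. The same formula reproduces all 16 sample sizes in the II.a table; a one-sided alpha gives 16 here. Allowing for attrition, 19/0.75 = 25.3, so 26. Power at n = 19 is Φ(0.75 × √19 − 1.96) = 90.5%.

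**Step 2: the comparison III.b describes.** For Arm 1 versus Arm 2, still assuming independence, power is Φ(0.75 × √(19/2) − 1.96) = 63.7%. For 90% power, n per arm is 2 × 18.7 = 37.4, so 38.

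**Step 3: add clustering in Arm 1 only.** The design effect is DE = 1 + (m − 1) × ICC.
- Pre-post power = Φ(0.75 × √(19/DE) − 1.96).
- Between-arm power = Φ(0.75 × √(19/(1 + DE)) − 1.96).
- False-positive rate of a test that ignores class = 2 × [1 − Φ(1.96/r)], with r = √((1 + DE)/2) between arms and r = √DE for Arm 1 pre-post.

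| Class size m | ICC | DE | Pre-post power | Between-arm power | False positives, between arms | False positives, Arm 1 pre-post |
|---|---|---|---|---|---|---|
| any | 0 | 1.00 | 90.5% | 63.7% | 5.0% | 5.0% |
| 4 | 0.02 | 1.06 | 88.8% | 62.5% | 5.3% | 5.7% |
| 4 | 0.05 | 1.15 | 86.2% | 60.6% | 5.9% | 6.8% |
| 4 | 0.10 | 1.30 | 81.8% | 57.8% | 6.8% | 8.6% |
| 2 | 0.02 | 1.02 | 89.9% | 63.3% | 5.1% | 5.2% |
| 2 | 0.05 | 1.05 | 89.1% | 62.7% | 5.3% | 5.6% |
| 2 | 0.10 | 1.10 | 87.6% | 61.6% | 5.6% | 6.2% |

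Simulated t-tests with 20 completers per arm and class effects in Arm 1 only agree to within about 0.2 points. With classes of 4 they give 5.2 to 6.8% between arms and 5.6 to 8.4% for Arm 1 pre-post. With classes of 2 they give 5.1 to 5.7% between arms.

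**Step 4: compare the two faults.** Using the pre-post formula for a between-arm comparison overstates power by 90.5 − 63.7 = 26.8 points. Clustering with classes of 4 then costs 63.7 − 62.5 = 1.2 to 63.7 − 57.8 = 5.9 points.

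**Step 5: what a class random effect can do.** With five classes of 4, the analysis-of-variance estimate of class variance is zero or negative in about 53%, 47% and 39% of simulated trials at ICC 0.02, 0.05 and 0.10. With small-sample degrees of freedom, simulated between-arm power falls from about 63 to 64% to 51 to 56%, and the false-positive rate is about 4%.

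**The case against.** The strongest reply is that no within-class correlation has been shown. Camaraderie as an aim and cohesion as a measure do not establish that change in a timed walking test correlates among classmates. The identical curriculum, the common instruction given to instructors and the make-up classes at other dojos would all tend to dilute a class effect. If both schedules ran at every dojo, classes of about 2 would leave almost nothing to correct. Ignoring dojo as a stratum also pushes the error in the opposite direction. All of this stands, and it is why the point is conditional and the size modest. It does not remove the structural omission: the plan creates groups in one arm and nowhere says how that is handled.

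A reader might infer that Arm 2 exercises individually. The documents say only usual exercise. The entry criteria bar recent martial arts and boxing programs but not other group exercise. What they support is that Arm 2 has no study-delivered classes before month 6, and the argument needs no more than that.

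A reader might also posit very uneven classes, since subjects choose their dojo, and obtain larger effects. No class sizes are given, so such a split would be a guess.

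**Conclusion.** The point holds in conditional form. Neither II.a nor III.b allows for group delivery in Arm 1, and any positive within-class correlation would make Arm 1's standard error too small and the stated power too high. Over an assumed ICC of 0.02 to 0.10 the effect on the between-arm test is small: at most about 1.8 points of excess false positives with classes of 4, and 0.7 with classes of 2. It is larger for an Arm 1 pre-post test, which matters because the first hypothesis and the power statement are both framed as change after classes.

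Two stronger conclusions are not supported. The documents do not show that Arm 1's error bars are in fact too narrow, because they contain no ICC. Nor is clustering the main reason the 90% is too high: the one-sample formula is the larger, separate fault. Correcting only for clustering would leave a figure of 82 to 89% when the planned comparison has about 58 to 62%. These figures rest on the plan's SD of 4.0 s, equal classes and a two-sided 5% level.

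**What to change.** **Section II.a.** Restate power for the Arm 1 versus Arm 2 comparison, and show it over an ICC range of 0.02 to 0.10 at the expected class size, which should be stated.

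**Section III.b.** Specify a between-arm analysis of month-6 change that accounts for dojo as the randomization stratum. Beside it, report a sensitivity analysis with a random effect for assigned class (dojo and schedule, ignoring make-up attendance) in the karate arm only, with small-sample degrees of freedom. State that with about five classes the class variance is poorly estimated, and that this analysis can be conservative and lose about 8 to 12 points of power; for that reason it should not replace the main analysis. At month 12 Arm 2 is also in classes, so the class term would apply there too.

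**Cost.** Wording, a record of each subject's assigned class and a little analysis time. The stated power will fall well below 90%, mostly because of the change of formula, and the sensitivity interval may be noticeably wider than the main one. This point does not itself call for more participants.
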